# Protocol and Statistical Analysis Plan

## Study Protocol

### Objectives

This research tests the effects of the mere presence of guns in the mass media (e.g. movies, video games, TV programs) on children. We predict that seeing guns in the mass media will increase subsequent aggression, and will lead to more positive attitudes about guns.

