### Experiment

Participants will be children 8-12 years old. Children will be tested in pairs. Each child will bring a sibling, relative, or friend to the study. Participants and partners will each receive a \$25 gift card. The design is a 2 (watch vs. play) by 3 (non-violent, violent with swords, violent with guns) between-subjects design. The outcome variables are the time spent handling a gun (in seconds), the number of times the trigger is pulled, and the number of times the trigger is pulled while pointing the handgun at oneself or another. After filling out a pre-test survey measuring trait aggression and media diet, one participant will be randomly assigned to play a video game while the other watches. The video game participants will play is a modified version of *Minecraft*. The participant pairs will be randomly assigned to one of three conditions: a non-violent condition with no weapons and no monsters, a violent condition with swords and monsters, and a violent condition with guns and monsters. Participants will play for 20 minutes, after which they will fill out a survey measuring their familiarity with *Minecraft* and their opinion toward the game.

After completing the survey, participants will be placed in a room containing games and toys, with hidden cameras. Participants will be told that they can play with any of the games and toys in the room

for the next 20 minutes. The toys and games will be in two drawers of a cabinet, while the bottommost drawer will contain two Sig Sauer P250 handguns. The handguns have been disabled and are unable to fire. In addition, a counter is placed inside the magazine well to count the number of times the trigger is depressed with enough force to discharge the handgun. This allows us to distinguish reliably the children who pull the trigger from those who handle the gun but do not pull the trigger. Parents will be asked to predict whether their child will handle the real gun and pull the trigger. The researcher and the parents will be able to watch the session via a monitor in a control room. After 20 minutes, the participants will fill out a survey on their attitudes toward guns. A thorough debriefing will follow.

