We predict that participants who play the game with guns will handle the gun longer, pull the trigger more times, and point the gun at oneself or another and pull the trigger more times than participants in the other conditions. One week after a child participates in Experiment 3, the researcher will call or email the parent to follow up.

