### **Attitudes Toward Guns**

To measure participants' attitudes toward guns, we will use the 15-item Attitudes Towards Guns and Violence Questionnaire (see Appendix C)vi, which has been validated on children 6-17 years old and young adults.vii It contains three subscales: *Comfort With Aggression* (e.g., "I don't like being around people with guns because someone could end up getting hurt" and "I wish everyone would get rid of all their guns"), *Excitement* (e.g., "I bet it would feel really cool to walk down the street with a gun in my pocket" and "I think it would be fun to play around with a real gun"), and *Power/Safety* (e.g., "Carrying a gun makes people feel powerful and strong" and "Carrying a gun makes people feel safe"). Items are scored using a 5-point scale (1=*Strongly disagree* to 5=*Strongly agree*). We will also measure whether the child has ever fired a gun, and whether the child has taken a gun safety class.

Prior to the experiment, parents will rate their child's level of interest in real guns using a 5-point scale (1=*no interest* to 5=*very interested*), as in previous research.viii

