## Statistical Analysis Plan

Data will be collected in three ways: parental consent is collected directly by Qualtrics; the participants' survey responses are done by hand on paper, and the participants' handling of the handguns is recorded as video. After the conclusion of the study, the paper responses will be uploaded by the research staff into a Qualtrics survey. The videos will be content analyzed by trained research assistants who observe the participants' behavior, verify the trigger pull count, and note if the trigger is depressed while the handguns are pointed at oneself or the other participant. At this point, the data can be merged into a single dataframe for validation and cleaning. Cleaning will be done in Excel and R.

Once the data has been cleaned, the variables will each be examined via summary statistics and visually. If necessary, variables will be transformed to conform to the assumptions of the statistical tests, the Cronbach's alpha of the survey batteries will be calculated, potential outliers will be identified, and preliminary bivariate and chi-squared tests will be run on the outcome variables. In addition, the three conditions will be tested for differences in the subjects along the measured variables.

After this, the dataframe will be imported into STATA to perform a generalized estimated equation (GEE) with an exchangeable correlation structure was used to analyze data, with pairs as unit of analysis. All outcome variables will be measured with a negative binomial log-link model. First, each outcome variable will be tested with the condition as the sole predictor variable. Next, each control variable (trait aggression, attitude toward guns, etc.) will be tested along with the condition. Finally, the full model will include condition and all of the control variables. The research team will find the model of best fit, though only the reduced (condition only) and full models (condition, gender, age, whether the participant had taken a firearm safety course, if there is a firearm in the home, attitudes toward guns, trait aggression, consumption of violent media, parental estimation of child's interest in firearms) will be reported.

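### The predicted effect on attitudes toward guns has no prespecified test in the game experiment, although the data to test it are collected

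*Combined protocol and SAP*

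**What the plan says.** The Objectives section states: "We predict that seeing guns in the mass media will increase subsequent aggression, and will lead to more positive attitudes about guns". Under Attitudes Toward Guns, the instrument is named: "we will use the 15-item Attitudes Towards Guns and Violence Questionnaire". It has three subscales and a five-point agreement scale. That section says neither whether a total score is formed nor which subscale would lead.

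The Experiment section places the questionnaire after the game and after the session in the room with the disabled handguns: "After 20 minutes, the participants will fill out a survey on their attitudes toward guns". The same section's outcome list begins: "The outcome variables are the time spent handling a gun (in seconds), the number of times the trigger is pulled". Its third and last entry is trigger pulls while the gun points at oneself or another child. The prediction for the gun condition begins "We predict that participants who play the game with guns will handle the gun longer, pull the trigger more times" and stays behavioural to its end.

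In the SAP the score appears as a covariate: "Next, each control variable (trait aggression, attitude toward guns, etc.) will be tested along with the condition". It appears again in the covariate list of the full model. Of the fitted models, only the condition-only and full models are to be reported. On the form of the model, the SAP says: "All outcome variables will be measured with a negative binomial log-link model".

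**The concern.** An objective should lead to an outcome, and an outcome to an analysis. Here the attitude prediction leads to a questionnaire and stops. A team that follows the SAP exactly will report handling time and the two trigger counts by condition, with attitudes on the right-hand side of the full model. It will report no estimate of the effect of condition on attitudes.

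If a comparison is added once the data have been seen, the choices of total or subscale, contrast, covariates and model are all open, and a reader cannot tell whether the result influenced them. Adding attitudes to the outcome list without further change would not be enough. The sentence on model form would then apply a count model to a bounded rating-scale score.

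**Working it through.** The main check is a trace of the attitude score through the document.

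1. **Prediction.** Objectives: attitudes are one of two predictions.
2. **Measurement.** Attitudes Toward Guns and Experiment: the questionnaire is given after exposure, in all three conditions.
3. **Outcome list.** Experiment: three outcomes, none of them attitudes.
4. **Specific predictions.** Experiment: handling time and trigger pulls only.
5. **Preliminary tests.** SAP: bivariate and chi-squared tests are planned on the outcome variables. By step 3 these do not include attitudes.
6. **Comparison of conditions.** SAP: the three conditions are to be compared on the measured variables. Attitudes could fall within this, but neither the score nor a test is named. It sits among the data-cleaning steps and reads as a comparability check.
7. **Models.** SAP: attitudes are a control variable. No model has them as the response.
8. **Other text.** Behavioral Measure of Aggression predicts the highest pro-gun attitudes after a violent clip with guns, through two main effects and a violence-by-guns interaction. That needs four cells. The game experiment has three: non-violent without weapons, violent with swords, violent with guns. There is no non-violent cell with guns, so the interaction cannot be estimated and this text supplies no analysis here.

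The plan's one relevant figure is the sample size. With a medium effect taken as d = 0.5 (not stated in the plan), two-sided 0.05 and power 0.80, the normal approximation gives 63 per group. The exact t-test gives 63.77, so 64, and 3 × 64 = 192. The plan's figures reproduce. The calculation names no outcome, so it does not bear on whether attitudes are tested.

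It does allow a rough look at what an attitude comparison could detect. Pairs are randomised, so the design effect is 1 + (2 − 1) × ICC and the effective n per group is 64 / (1 + ICC). The ICC is not given; 0 to 0.5 is assumed. For guns against one other condition, power is Φ(0.5 × √(n/2) − z), with z = 1.96 at 0.05 and z = 2.24 when 0.05 is split over two comparisons. For example, at ICC 0.3, n = 64 / 1.3 = 49.2, 0.5 × √24.6 = 2.48, and Φ(2.48 − 1.96) = 0.70.

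| ICC (assumed) | Effective n per group | Power, one comparison at 0.05 | Power, each of two at 0.025 |
|---|---|---|---|
| 0 | 64.0 | 0.81 | 0.72 |
| 0.2 | 53.3 | 0.73 | 0.63 |
| 0.3 | 49.2 | 0.70 | 0.60 |
| 0.5 | 42.7 | 0.64 | 0.53 |

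Under these assumptions a comparison is feasible but not strongly powered, which fits a secondary outcome.

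**The case against.** The strongest defence is that the document covers a programme. The Objectives section speaks of movies, video games and television; other sections mention Experiments 1, 2 and 3. The attitude prediction may belong to the clip experiments, as the noise-blast measure of aggression does. On that reading the game experiment's predictions and outcome list agree with each other, and the fault is leftover text. This is a fair reading, and it is why narrowing the objective is an acceptable remedy. It does not remove the gap: the objective is stated without that limit, and the questionnaire is given in this experiment.

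It is also true that attitudes are treated as a dependent variable elsewhere and that the SAP's check on measured variables could reach them. So a reader should not infer that the score is nothing but a control variable throughout the document. That holds for its named role in the SAP.

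Two further inferences are tempting.

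- The example items differ in direction: agreement with some is anti-gun, with others pro-gun. A reader might conclude that the scoring is wrong and that effects would cancel. The section gives response anchors, not a scoring key. It refers to an appendix and a published manual that are not available here, and it defines no total. The planned Cronbach's alpha might also expose unrecoded items. The documents support neither a scoring error nor a size for one.
- Background and Rationale might be read as repeating the attitude prediction. It predicts interest in acquiring and using guns after films, which is a related but different construct.

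Finally, the count-model point is conditional. It applies only if attitudes are added as an outcome under the present wording.

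**Conclusion.** The point holds as a gap in prespecification. One of the two predictions in the Objectives section has no named outcome, score, contrast or model in the game experiment, and the reported models all have other responses.

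A reader might go further and infer that the trial cannot confirm or refute the attitude prediction. The documents do not support that: the questionnaire is collected after exposure in every randomised condition, so a randomised comparison can be made. The condition-only analyses of the three behavioural outcomes are unaffected.

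The conclusion rests on the text alone and needs no numerical assumption. The power figures are illustrative and depend on the assumed d = 0.5 and ICC range.

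**What to change.** Either test the prediction or withdraw it for this experiment.

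**To test it**, in the Experiment section and the SAP:

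- Name the attitude score as a secondary outcome, scored by the instrument's own key so that higher means more pro-gun. State whether the total or a particular subscale is used.
- Compare guns with each of the other two conditions, and state how multiplicity is handled. Guns versus swords addresses guns within violent play; guns versus non-violent also carries the effect of violence.
- Use the planned exchangeable GEE on pairs, with Gaussian family and identity link, and without covariates measured after exposure that condition could have changed.
- Limit the negative binomial sentence to the three behavioural outcomes.
- State that the estimate is the total effect of condition on attitudes measured after the gun-room session, so it includes any effect of that session.

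**To withdraw it**, remove the attitude prediction from this experiment's objective.

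In either case, reconcile Objectives, Experiment, Behavioral Measure of Aggression and the SAP, and make the change before the data are examined by condition. The cost is a few sentences and one additional model on data already planned. The downside is one more secondary outcome.

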### Background and Rationale

On 14 December 2012, after shooting his mother, 20-year-old Adam Lanza shot and killed 20 children and 6 employees in Sandy Hook elementary school, in Newtown, Connecticut. In the wake of the Newton shootings, there has been considerable discussion about gun violence. What is conspicuously absent from these discussions, however, is the fact that just *SEEING* guns can increase aggression.i This effect, called the “weapons effect,” has been replicated in over 50 other studies.ii The effect occurs for angry and non-angry individuals, both inside and outside the lab.

A recent analysis of top selling films found that the depiction of guns in violent scenes in PG-13 films that target youth has increased from the level of G and PG files in 1985 when the rating was introduced, to the level of R films by 2005, to exceed the level of R films since 2012.iii By definition, a PG-13 movie is supposed to have less violence than an R-rated movie. The Motion Picture Association of America says on its website that the violence in a PG-13 movie “does not reach the restricted R category.” Our study shows that it does. By including guns in violent scenes, film producers may be inadvertently increasing aggression in youth via a weapons effect. Experiment 1 directly tests this hypothesis. Previous research has shown that when exposed to movie characters that smoke, many youth are more likely to start smoking themselvesiv; the same is true for characters that drinkv. Similarly, we predict that youth will be more interested in acquiring and using guns after exposure to gun violence in films. We also predict they will behave more aggressively following exposure to guns in movies.

### Experiment

Participants will be children 8-12 years old. Children will be tested in pairs. Each child will bring a sibling, relative, or friend to the study. Participants and partners will each receive a \$25 gift card. The design is a 2 (watch vs. play) by 3 (non-violent, violent with swords, violent with guns) between-subjects design. The outcome variables are the time spent handling a gun (in seconds), the number of times the trigger is pulled, and the number of times the trigger is pulled while pointing the handgun at oneself or another. After filling out a pre-test survey measuring trait aggression and media diet, one participant will be randomly assigned to play a video game while the other watches. The video game participants will play is a modified version of *Minecraft*. The participant pairs will be randomly assigned to one of three conditions: a non-violent condition with no weapons and no monsters, a violent condition with swords and monsters, and a violent condition with guns and monsters. Participants will play for 20 minutes, after which they will fill out a survey measuring their familiarity with *Minecraft* and their opinion toward the game.

After completing the survey, participants will be placed in a room containing games and toys, with hidden cameras. Participants will be told that they can play with any of the games and toys in the room

for the next 20 minutes. The toys and games will be in two drawers of a cabinet, while the bottommost drawer will contain two Sig Sauer P250 handguns. The handguns have been disabled and are unable to fire. In addition, a counter is placed inside the magazine well to count the number of times the trigger is depressed with enough force to discharge the handgun. This allows us to distinguish reliably the children who pull the trigger from those who handle the gun but do not pull the trigger. Parents will be asked to predict whether their child will handle the real gun and pull the trigger. The researcher and the parents will be able to watch the session via a monitor in a control room. After 20 minutes, the participants will fill out a survey on their attitudes toward guns. A thorough debriefing will follow.

We predict that participants who play the game with guns will handle the gun longer, pull the trigger more times, and point the gun at oneself or another and pull the trigger more times than participants in the other conditions. One week after a child participates in Experiment 3, the researcher will call or email the parent to follow up.

### **Attitudes Toward Guns**

To measure participants' attitudes toward guns, we will use the 15-item Attitudes Towards Guns and Violence Questionnaire (see Appendix C)vi, which has been validated on children 6-17 years old and young adults.vii It contains three subscales: *Comfort With Aggression* (e.g., "I don't like being around people with guns because someone could end up getting hurt" and "I wish everyone would get rid of all their guns"), *Excitement* (e.g., "I bet it would feel really cool to walk down the street with a gun in my pocket" and "I think it would be fun to play around with a real gun"), and *Power/Safety* (e.g., "Carrying a gun makes people feel powerful and strong" and "Carrying a gun makes people feel safe"). Items are scored using a 5-point scale (1=*Strongly disagree* to 5=*Strongly agree*). We will also measure whether the child has ever fired a gun, and whether the child has taken a gun safety class.

Prior to the experiment, parents will rate their child's level of interest in real guns using a 5-point scale (1=*no interest* to 5=*very interested*), as in previous research.viii

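### The full model leaves out the child's prior-firing history without a reason (a small precision loss) and adjusts for a gun-attitude score taken after the gun session (the larger problem)

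*Combined protocol and SAP*

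**What the plan says.** The protocol section Attitudes Toward Guns collects two gun-history items in one sentence: "We will also measure whether the child has ever fired a gun, and whether the child has taken a gun safety class". It does not say when they are asked. The same section sets a baseline measure of gun interest: "Prior to the experiment, parents will rate their child's level of interest in real guns using a 5-point scale".

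The Statistical Analysis Plan defines the full model by a closed list. After condition, gender and age come "whether the participant had taken a firearm safety course, if there is a firearm in the home, attitudes toward guns, trait aggression", and the list ends with "consumption of violent media, parental estimation of child's interest in firearms) will be reported". Safety training is included. Prior firing is not, and no reason is given.

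The timing of the attitude score is clear from the Experiment section. The game comes first, then the session in the room with the handguns, and then: "After 20 minutes, the participants will fill out a survey on their attitudes toward guns". The Objectives treat attitudes as something exposure will alter: "We predict that seeing guns in the mass media will increase subsequent aggression, and will lead to more positive attitudes about guns". The section Behavioral Measure of Aggression, which describes Experiments 1 and 2, likewise predicts the highest pro-gun attitudes after violent content with guns.

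Before the full model there is a looser step: "Next, each control variable (trait aggression, attitude toward guns, etc.) will be tested along with the condition". A search for the best-fitting model is also planned, "though only the reduced (condition only) and full models" are to be reported.

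**The concern.** The covariate list leaves out a variable that is safe to adjust for and includes one that is not. Prior firing is a lifetime history that the assigned game cannot change. It is also plausibly related to handling a gun and pulling its trigger, although the documents do not say so. The attitude score follows both the exposure and the behaviour being analysed, and the protocol expects the exposure to move it.

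The stakes differ. Omitting a baseline covariate in a randomised comparison widens the interval somewhat. Adjusting for a variable that the condition affects changes what the condition coefficient estimates: it is no longer the whole effect of the game on behaviour. The SAP reports the condition-only and full models without saying which is primary, so a weaker condition effect in the full model could be read as confounding explained away.

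**Working it through.** **1. The plan's own figure.** Power Analysis states 64 per group for a medium effect at the .05 level with power .80. Taking medium as d = 0.5, a two-sided test and independent children, the two-sample t-test needs 63.77, rounded up to 64, with power 0.801. The total is 3 × 64 = 192. The stated figure reproduces, and no covariate enters it.

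**2. Adding prior firing.** Let R² be the share of residual outcome variance that prior firing explains beyond the other covariates. The documents give no value, so 0.01 to 0.10 is an assumption. Adjustment multiplies the residual SD by √(1 − R²), so the effective d is 0.5/√(1 − R²).

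| Assumed R² | Power at 64 per group | n per group for 80% power |
|---|---|---|
| 0 | 0.801 | 63.8 |
| 0.01 | 0.805 | 63.1 |
| 0.02 | 0.809 | 62.5 |
| 0.05 | 0.821 | 60.6 |
| 0.10 | 0.841 | 57.5 |

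The gain runs from 0.4 to 4 power points. Intervals narrow by 1 − √0.99 = 0.5% to 1 − √0.90 = 5.1%. Gun in the home, safety course and parent-rated interest are already in the model and probably overlap with prior firing, so the low end is more likely.

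**3. Adjusting for the attitude score.** Assume a total condition effect of 0.5 SD. Let a be the condition's effect on attitude in SD, and b the within-condition slope of outcome on attitude in SD per SD. Both are assumed to lie between 0.2 and 0.5. In a linear model:

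- adjusted effect = 0.5 − a·b, so the share removed is a·b/0.5;
- residual SD = √(1 − b²);
- for two equal groups, the squared correlation of condition with attitude is r² = (a²/4)/(1 + a²/4);
- effective d = (0.5 − a·b)·√(1 − r²)/√(1 − b²).

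| a | b | Adjusted effect | Share removed | Power at 64 per group |
|---|---|---|---|---|
| 0.2 | 0.2 | 0.46 | 8% | 0.746 |
| 0.2 | 0.5 | 0.40 | 20% | 0.732 |
| 0.3 | 0.3 | 0.41 | 18% | 0.665 |
| 0.5 | 0.2 | 0.40 | 20% | 0.604 |
| 0.5 | 0.5 | 0.25 | 50% | 0.349 |

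Worked case a = b = 0.5: 0.5 − 0.25 = 0.25; r² = 0.0625/1.0625 = 0.059; d = 0.25 × 0.970/0.866 = 0.28; power 0.349, against 0.801 unadjusted.

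The subtraction of a·b does not require attitude to cause behaviour. If handling the gun makes a child's attitudes more positive, b is again positive and the same loss follows.

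Steps 2 and 3 are linear approximations that ignore correlation within pairs. They indicate size and do not reproduce the planned negative binomial GEE.

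**The case against.** The strongest reply is that covariate choice in a randomised trial is largely the analyst's preference. Pairs are randomised, so omitting firing history brings no systematic bias, and the condition-only model is reported whatever the full model holds. Firing history may also appear in the balance check on measured variables, in the open-ended single-covariate step or in the best-fit search. Most of this stands, and it is why the omission is minor. The other steps do not repair it, however. If the balance check showed an imbalance in firing history, neither reported model could adjust for it, and adding it then would be a post hoc choice. The reply also does not touch the attitude score, which adding firing history would not cure.

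Three stronger readings are tempting, and the documents do not support them.

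- *The attitude score was chosen in place of firing history.* No substitution is described. The two are separate decisions in one list, which also keeps other gun-related baseline variables.
- *A strong predictor is being wasted.* The documents give neither the prevalence of prior firing nor its relation to the outcomes. Assume 25% prevalence, a rate ratio of 2 to 3, a mean of 3 and dispersion of 2. It then accounts for 0.12/2.33 = 5% to 0.33/2.33 = 14% of the variance term, but with no other covariate in the model. The increment beyond the listed covariates is what matters, and that is unknown.
- *Chance imbalance is a further harm on top of lost precision.* On the same inputs, an 8-point imbalance at ratio 3 shifts the rate ratio by (1 + 2 × 0.29)/(1 + 2 × 0.21) = 1.11, or 0.107 on the log scale. The standard error of the log rate ratio is √(2 × 2.33/64) = 0.27, or 0.33 with a within-pair correlation of 0.5. The shift is therefore 0.3 to 0.4 standard errors, which the standard error already reflects. It is the same cost counted a second time.

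**Conclusion.** The point holds as two linked defects of unequal weight. The unexplained absence of prior firing is a minor specification gap, with a cost limited to precision and probably close to the bottom of the range in step 2. The post-session attitude covariate is the more serious defect, because the full model's condition coefficient would no longer estimate the total effect of the assigned game.

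The timing of the attitude survey and its predicted response to exposure come from the protocol. The size of the loss depends on the assumed a and b. If the condition did not move attitudes at all, nothing would be removed, but that would contradict the protocol's own prediction. The condition-only model is free of the attitude problem.

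**What to change.** Make two separate changes to the full-model list before analysis.

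1. Add prior firing (yes/no), or state why it is left out. Record it on the parent's form before the session, alongside the parent's rating of interest in guns. A question to the child in the pre-test survey could cue guns before a session in which the handguns are left to be found.
2. Remove the post-session attitude score from the covariates, in the single-covariate step as well as the full model. Analyse it as an outcome, in line with the Objectives, and name a model suited to a rating-scale score, since the SAP assigns every outcome a negative binomial model. The parent's rating remains as the baseline measure of gun interest.

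The cost of the first change is one SAP line and one coefficient. If both changes are made and attitude would have entered as a single score, there is no net extra term. No new data are needed beyond fixing who answers the firing item and when. Analysing attitudes as an outcome needs a short added specification.
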